Unanticipated Adverse Device Effects (UADE)	22
Device Deficiencies	22
Investigational Products	23
Investigational Product Description	23
Investigational Product Labeling & Accountability	23

Regulatory, Ethical and Study Oversight Considerations	24
Regulatory and Ethical Considerations	24
Financial Disclosure	24
Informed Consent Process	24
Data Protection	25
Data Quality Assurance	25
Source Documents	25
Study and Site Closure	25
Publication Policy	26
Statistical Considerations	26
References	28
Glossary	28

1. Protocol Summary

Study Sponsor	Verily Life Sciences LLC
Study Description	
This study seeks to understand patient diagnostic and treatment journey and positive airway pressure (PAP) therapy compliance for Verily Sleep Apnea (VSA) program/app users. Participants will enroll remotely and may undergo a home sleep test (HST). Upon confirmation of obstructive sleep apnea (OSA) and prescription of PAP therapy, the participant will begin using the VSA app to supplement PAP treatment. After 90 days of active participation, the participant will be given instructions for follow-up care, as indicated.
 
This study will take a decentralized approach. Recruitment, enrollment, consultation, testing, coaching and active participation with the VSA app will take place remotely.

Study Objectives	
Primary:
 
• To assess and quantify patient journey (e.g., time to diagnosis, time to initiate therapy, patient satisfaction) for users of the VSA program 
Secondary:
 
• To assess patient journey completion rates for users of the VSA program• To assess and quantify PAP compliance in users of the VSA program 
[REDACTED]

Study Endpoints	
Primary
 
• Time (number of days) from when participant is told they may have OSA to OSA diagnosis
○ Time (number of days) from when participant is told they may have OSA to when they receive HST prescription○ Time (number of days) from when participant receives HST prescription to when they receive their diagnosis• Time (number of days) from OSA diagnosis to PAP therapy initiation• Time (number of days) from therapy initiation to when 90-day compliance threshold is achieved 
Secondary
 
• Completion rates
○ Among individuals who had an HST ordered, % of individuals who completed the HST○ Among individuals prescribed a PAP device, % of individuals who filled the order (PAP device delivered to them)○ Among individuals prescribed a PAP device, % of individuals who used the PAP device at least once during the 90 days• Compliance Metrics

	
 ○ Percent of participants who meet 90 day compliance success criteria, as defined by: 
 ■ ≥ 4 hours per night on 70% of nights during a consecutive 30 day period anytime during the first 90 days
Study Type	This is a single group, unblinded, prospective clinical study
Regulatory Status/Trial Classification	Non-significant risk (NSR)
Study Population	
Approximately 50-200 individuals who have been screened and diagnosed with Obstructive Sleep Apnea (OSA) during the study's initial screening and diagnostic process will be enrolled as participants in the study. This study will enroll remotely to participants across the United States.
 
The number of individuals who will have to be screened will be greater than the number ultimately enrolled, i.e., greater than 50-200. The number of individuals who undergo the screening process will depend on how many must be screened in order to identify the requisite 50-200 subjects who meet the diagnostic and other criteria for enrollment.

Participant Duration	For participants who are diagnosed with OSA and prescribed a PAP device, active participation in the study after receiving the PAP device is expected to last approximately 3 months from receipt of the device. Active participation is defined as using the PAP device (PAP data collection) while completing the other study related activities (including VSA app and console use, surveys/questionnaires, and interacting with optional Health Coaches)

	For participants who are diagnosed with OSA and prescribed a PAP device, total participation may last for up to one (1) year, including screening, time to diagnosis, and PAP data collection after active participation in the study has been completed.
Inclusion Criteria	
 1. Ages 18 or older 2. Able to speak and read English 3. Legal United States Resident with a Government Issued ID 4. Participating in the Project Baseline Community Study 5. Demonstrates understanding of the study requirements and is able and willing to sign the informed consent form 6. Own a smartphone with a data plan and be the primary user of the smartphone; smartphone must use Android Lollipop (5.1+ / API 22+) or iOS 11.X+ 7. Own a computer with a web camera 8. Consistent access to electricity and wifi for the duration of the study 9. Have a high risk of OSA as determined by screening questionnaire 10. Good candidate for PAP therapy, in the opinion of the managing clinician 11. Without significant limitation in ability to participate in the study, in the opinion of the investigator.
Exclusion Criteria	
 1. Previously diagnosed with sleep apnea or other sleep disorders, that in the opinion of the investigator, makes the participant ineligible (e.g., Obstructive Sleep Apnea, Central Sleep Apnea, Complex Sleep Apnea, chronic insomnia) 2. Participant is a shift worker (indicated by having a night shift schedule on a regular basis, or a work shift that changes or rotates on a daily, weekly, or monthly basis) 3. Sponsor employees and individuals working on Project Baseline 4. Self reported to be pregnant or planning to become pregnant during the study period 5. Current use of home oxygenation devices, such as supplemental oxygen

[REDACTED]

[REDACTED]	[REDACTED]	[REDACTED]	[REDACTED]
[REDACTED]	[REDACTED]	[REDACTED]	[REDACTED]
[REDACTED]	[REDACTED]	[REDACTED]	[REDACTED]
[REDACTED]	[REDACTED]	[REDACTED]	[REDACTED]
[REDACTED]	[REDACTED]	[REDACTED]	[REDACTED]
[REDACTED]	[REDACTED]	[REDACTED]	[REDACTED]

[REDACTED]

[REDACTED]

[REDACTED]	[REDACTED]	[REDACTED]	[REDACTED]
7	[REDACTED]	[REDACTED]	[REDACTED]

3. Prior Experience

[REDACTED]

4. Study Background and Rationale

4.1. Background

Obstructive sleep apnea (OSA) is a sleep breathing disorder that affects an estimated 54 million Americans (calculated based on a 16-country prevalence data study),^{1,2} and is associated with heart disease, stroke, type 2 diabetes and other life-threatening conditions. Despite the condition's high prevalence and increasing public awareness, past research has shown that approximately 80 percent of individuals with OSA are undiagnosed,³ untreated and therefore unaware of their own risk and of the benefits that therapy could provide.

OSA presents to the patient most frequently as excessive daytime tiredness, increased lapses or micro-sleeps during important activities such as driving, nighttime disturbances to bed partners (largely through snoring or restlessness)⁴, and perhaps most importantly significantly increased risk and severity of multiple comorbidities including but not limited to cardiovascular disease (CVD)⁵⁻⁶, type 2 diabetes (T2D)⁷, and mental health disorders⁸.

The diagnosis pathway for patients with OSA is often complex and difficult for patients to navigate, involving interactions with many different parties such as a primary care provider, sleep labs, durable medical equipment companies, and insurance providers⁹. There exist opportunities for better coordinating care and improving the patient experience in the diagnostic and treatment pathways.

The gold standard treatment for OSA is the night-time use of a positive airway pressure (PAP) device. PAP provides positive pressure to support a patent airway for patients who experience clinically significant frequency of apneas and/or hypopneas¹⁰. The PAP device consists of a bedside powered device that pushes air through a flexible tube to a mask worn either over the mouth and nose or just the nose. This device is, as can readily be imagined, difficult to introduce into the patient's bedtime routine, life, travel, etc. No other treatment or therapy for OSA has been shown to be as effective as PAP¹¹. Any method of increasing compliance with the patient's

prescribed therapy could thus decrease both the cost of care for relevant comorbidities as well as significantly improve the patient's quality of life.

4.2. **Rationale**

This study seeks to understand patient journey and PAP therapy compliance for Verily Sleep Apnea (VSA) program users.

The VSA app is intended to help individuals who may have OSA go through the complex diagnostic pathway more efficiently and virtually. The VSA app is also intended to help patients who have been diagnosed with OSA to manage their therapy and is intended to facilitate a program where users can possibly discover their potential risk for OSA through a clinically validated questionnaire screener and consult with a healthcare professional.

The VSA app will also allow participants to message with Health Coaches who will provide guidance related to sleep and OSA. Communication between the Health Coach and participant is important in enhancing and promoting motivation for PAP adherence. The motivational enhancement approach is a published behavioral intervention based on the principles of motivational interviewing¹². Its fundamental premise is to honor the natural ambivalence that accompanies any change to behavior and to approach the patient in a thoughtful and empathetic manner that elicits critical thought - in order to maximize behavior change.

Technology, especially mobile technology, has the potential to provide new, easier to use, more timely, and more scalable methods for helping patients discover their OSA risk, onboarding patients with OSA to PAP treatment, as well as helping these patients to troubleshoot and make progress in their OSA treatment.

5. **Study Design**

5.1. **Study Objectives and Endpoints**

5.1.1. **Objectives(s)**

Primary:

- To assess and quantify patient journey (e.g., time to diagnosis, time to initiate therapy, patient satisfaction) for users of the VSA program

Secondary:

- To assess patient journey completion rates for users of the VSA program
- To assess and quantify PAP compliance in users of the VSA program

[REDACTED]

5.1.2. **Endpoint(s)**

Primary

- Time (number of days) from when participant is told they may have OSA to OSA diagnosis

- Time (number of days) from when participant is told they may have OSA to when they receive HST prescription
 - Time (number of days) from when participant receives HST prescription to when they receive diagnosis
- Time (number of days) from OSA diagnosis to PAP therapy initiation
- Time (number of days) from therapy initiation to when 90-day compliance threshold is achieved

Secondary

- Completion rates
 - Among individuals who had an HST ordered, % of individuals who completed the HST
 - Among individuals prescribed a PAP device, % of individuals who filled the order (PAP device delivered to them)
 - Among individuals prescribed a PAP device, % of individuals who used the PAP device at least once during the 90 days
- Compliance Metrics
 - Percent of participants who meet 90 day compliance success criteria, as defined by:
 - ≥ 4 hours per night on 70% of nights during a consecutive 30 day period anytime during the first 90 days

[REDACTED]

[REDACTED]

[REDACTED]

[REDACTED]

[REDACTED]

[REDACTED]

[REDACTED]

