5.2. Overview

This is a single group, unblinded, prospective clinical study to understand the patient diagnostic and treatment journey and PAP therapy compliance for Verily Sleep Apnea (VSA) program users. Participants will enroll remotely and if deemed clinically appropriate will undergo a commercially available and approved home sleep test (HST). Upon confirmation of OSA, the participant will begin using the VSA app to supplement PAP treatment. After 90 days of active participation or in the event of earlier departure from the study, the participant will be given instructions for follow-up care, as indicated. Participants will lose access to the VSA app at the end of the 90 day period.

This study will take a decentralized approach. Recruitment, enrollment, consultation, coaching and active participation with the VSA app will take place remotely.

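### Does the missing day 0 for the 90-day PAP compliance window distort the compliance rate or make the ever-used rate 100% by construction?

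*Combined protocol and SAP*

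**What the plan says.** Section 5.1.2 (repeated in the Section 1 summary) has three endpoints that refer to 90 days:

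- Secondary, compliance rate: "≥ 4 hours per night on 70% of nights during a consecutive 30 day period anytime during the first 90 days".
- Secondary, completion: "Among individuals prescribed a PAP device, % of individuals who used the PAP device at least once during the 90 days".
- Primary, time to compliance: "Time (number of days) from therapy initiation to when 90-day compliance threshold is achieved". Section 12 repeats it.

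None of them names day 0, and the visible text does not define therapy initiation.

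The Participant Duration row of Section 1 says that "active participation in the study after receiving the PAP device is expected to last approximately 3 months from receipt of the device". Its next sentence reads "Active participation is defined as using the PAP device (PAP data collection) while completing the other study related activities". The same row allows total participation of up to one year, including "PAP data collection after active participation in the study has been completed". Section 5.2 sets the point for follow-up instructions at "After 90 days of active participation or in the event of earlier departure from the study", and adds: "Participants will lose access to the VSA app at the end of the 90 day period".

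Text is blacked out after the compliance criterion in Section 5.1.2, in Section 6.2.5, throughout Section 6.3 (test procedures and data collection) and in Section 12 after the estimation method.

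**The concern.** Delivery and first use are different events, and Section 5.1.2 has a separate completion rate for each. A 90-day clock could start at either.

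If it starts at receipt, someone who leaves the device in its box for some weeks has fewer nights in which to reach the threshold, while the primary time is still counted from initiation. Slow starters would then be less likely to count as compliant for a reason unrelated to how well they use the device.

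If it starts at first use, everyone with a window has by definition used the device, so the ever-used rate might appear to be 100%, and people who never start have no window.

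Section 12 expects no hypothesis testing, so the estimates and their confidence intervals are what the study produces. Two analysts choosing different origins could report different compliance rates.

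**Working it through.** **Inputs from the protocol.** A 30-day period, 70% of nights, a 90-day window, and planned enrolment of about 50–200. The protocol gives no expected compliance rate or start delay, so there is no planned figure to reproduce.

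**Assumptions, not in the protocol.** The delay d from receipt to first use, and the nightly probability of at least 4 hours once started. Nights are independent given the person.

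**1. Counting.**
- Nights needed: 0.70 × 30 = 21.
- 30-day windows in 90 days: 90 − 30 + 1 = 61.
- With receipt as day 0 and a delay of d days: 90 − d nights remain, with 61 − d full windows after the start.
- d = 14 gives 76 nights and 47 windows. d = 30 gives 60 nights and 31 windows. d = 60 gives 30 nights and 1 window.
- At d = 70 only 20 nights remain, so 21 cannot be reached.
- With first use as day 0, every starter has 90 nights and 61 windows.

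**2. Effect on the compliance rate if receipt is day 0.** Simulated chance that some 30-day window holds at least 21 compliant nights, with every participant delayed by d:

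| Assumed nightly use | d = 0 | d = 14 | d = 30 | Loss at 14 / 30 days (points) |
|---|---|---|---|---|
| Beta(3,2) across people | 58.7% | 56.4% | 53.0% | 2.3 / 5.7 |
| Beta(1.8,1.2) across people | 58.1% | 56.1% | 53.8% | 2.0 / 4.3 |
| Same p = 0.60 for all | 71.1% | 63.3% | 51.3% | 7.8 / 19.8 |
| Logit N(0, 1.2), rising 0.5 per 30 days | 70.7% | 63.8% | 54.8% | 6.9 / 15.9 |
| Logit N(0, 1.2), no trend | 41.6% | 40.5% | 37.6% | 1.1 / 4.0 |
| Logit N(0, 1.2), falling 0.5 per 30 days | 25.6% | 25.4% | 25.5% | 0.2 / 0.1 |

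At d = 7, Beta(3,2) gives 57.6%, a loss of 58.7 − 57.6 = 1.1 points.

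The large losses come only from giving every person the same nightly probability or from assuming that use improves steadily. If use declines, the first weeks decide the outcome and the lost days at the end cost almost nothing.

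**3. From a uniform delay to a study rate.** The loss in the study rate is the share delayed times the loss at that delay. As an illustration, if a quarter start 30 days late and the rest at once, Beta(3,2) gives 0.25 × 5.7 = 1.4 points.

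**4. Scale.** The 95% half-width at a rate of 58% is 1.96 × √(0.58 × 0.42 / n): 13.7 points at n = 50 and 6.8 at n = 200.

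**5. Ever-used rate.** The denominator is everyone prescribed a device. If 80% start, the rate is 40/50 or 160/200 = 80%, whichever origin is used. It becomes 100% only if people without a first-use date are removed, which contradicts the stated denominator.

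**6. Does any text set receipt as the origin of the compliance window?** The Participant Duration row gives an approximate, expected length of participation, and its next sentence equates active participation with using the device. It does not govern the endpoint. If therapy initiation means set-up or receipt, it agrees with that row. If it means first use, the compliance rate and the time to threshold share that origin. Neither reading makes two endpoint definitions contradict each other.

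**The case for a change.** The strongest case for a change is that time to threshold is a primary endpoint, that the compliance rate is the only compliance metric visible, and that the text leaves a real choice between two origins. A start more than a month late is penalised heavily under receipt, and a start 70 or more days late cannot succeed. Sections 5.3 and 12 describe enrolment of people who begin PAP therapy, which a careless analyst might take as the analysis set for the ever-used rate. The repair would be only wording, and PAP data are collected after active participation, so 90 nights from first use should be obtainable.

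The ambiguity stands, and so does the arithmetic on late starts. The claim that a stated rule yields a wrong result does not stand. First use is not plainly the better origin either. App access ends with the 90 days of active participation (Sections 5.2 and 6.2.5), so if those days run from receipt, a window from first use would take in nights without the app for late starters. Receipt keeps the window inside the supported period but makes it shorter for them. That is a trade-off between two reasonable estimands.

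People who never reach the threshold have no time to enter an average. That question arises under any origin and is separate from this one.

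**Conclusion.** No change to the plan follows. The visible text leaves day 0 and therapy initiation unwritten, and an analyst would fill both sensibly with receipt or first use and report which was used. The definition may also already stand in the redacted parts of Sections 5.1.2, 6.3 or 12. The ever-used rate is not a tautology, because its denominator is fixed as everyone prescribed.

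The choice of origin moves the compliance rate by about 2 points at a 14-day delay and 4–6 points at 30 days under the Beta spreads, if all participants are that late. Across the other models tried, the loss runs from almost nothing to about 20 points at 30 days. The protocol supports neither the delays nor the use patterns behind these figures. If most people start within a week or two and nightly use varies between people without a strong upward trend, the effect is small beside half-widths of roughly 7–14 points. The study is descriptive, so no test or error rate depends on it. The conclusion would weaken if many participants began a month or more after receipt and their use rose steadily afterwards.

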5.2. Overview

This is a single group, unblinded, prospective clinical study to understand the patient diagnostic and treatment journey and PAP therapy compliance for Verily Sleep Apnea (VSA) program users. Participants will enroll remotely and if deemed clinically appropriate will undergo a commercially available and approved home sleep test (HST). Upon confirmation of OSA, the participant will begin using the VSA app to supplement PAP treatment. After 90 days of active participation or in the event of earlier departure from the study, the participant will be given instructions for follow-up care, as indicated. Participants will lose access to the VSA app at the end of the 90 day period.

This study will take a decentralized approach. Recruitment, enrollment, consultation, coaching and active participation with the VSA app will take place remotely.

5.3. Sample Size and Number of Participating Sites

The study plans to enroll approximately 50-200 individuals that will be diagnosed with Obstructive Sleep Apnea (OSA) and begin PAP therapy, as part of the study procedures. This study will enroll remotely to participants across the United States.

5.4. Inclusion Criteria

1. Ages 18 or older
2. Able to speak and read English
3. Legal United States Resident with a Government Issued ID
4. Participating in the Project Baseline Community Study
5. Demonstrates understanding of the study requirements and is able and willing to sign the informed consent form
6. Own a smartphone with a data plan and be the primary user of the smartphone; smartphone must use Android Lollipop (5.1+ / API 22+) or iOS 11.X+
7. Own a computer with a web camera
8. Consistent access to electricity and wifi for the duration of the study
9. Have a high risk of OSA as determined by screening questionnaire
10. Good candidate for PAP therapy, in the opinion of the managing clinician
11. Without significant limitation in ability to participate in the study, in the opinion of the investigator.

5.5. Exclusion Criteria

1. Previously diagnosed with sleep apnea or other sleep disorders, that in the opinion of the investigator, makes the participant ineligible (e.g., Obstructive Sleep Apnea, Central Sleep Apnea, Complex Sleep Apnea, chronic insomnia)
2. Participant is a shift worker (indicated by having a night shift schedule on a regular basis, or a work shift that changes or rotates on a daily, weekly, or monthly basis).
3. Sponsor employees and individuals working on Project Baseline
4. Self reported to be pregnant or planning to become pregnant during the study period
5. Current use of home oxygenation devices, such as supplemental oxygen

5.6. Discontinued/Withdrawal of Study Subjects

Participation in this research study is voluntary and participants may withdraw at any time. In the event the participant chooses to withdraw, he/she will be instructed to contact the Investigator immediately and will be asked the reason for their withdrawal from the study.

The participant may also be discontinued from the research study at any time if the Investigator considers it to be in his/her best medical interest. The Investigator may withdraw the participant any time due to the non-compliance with respect to the provisions of the protocol. If a participant withdraws prior to study completion, no new health information identifying him/her will be gathered after that date. Information that has been gathered may still be used and given to others.

If an enrolled participant withdraws or is discontinued prior to completing all study activities, a new, qualified candidate may be enrolled in the study to compensate for the incomplete data set.

Participants will either satisfactorily complete all requirements set forth in the protocol or their participation in the clinical study will be prematurely terminated. The completion of a participant's participation in the study or early departure from the study, including reasons for early discontinuation, will be fully documented on the appropriate case report form and an effort will be made to connect them with a local clinician for post-study consultation, instructions and, if indicated, recommendations for follow-up care.

6. Study Assessment Plan and Methods

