participants will be instructed to contact their DME provider. The DME provider may provide a replacement device or repairs at the sponsor’s discretion. Alternatively, the sponsor may choose to exit the participant without providing a replacement device.

The sponsor will not provide maintenance or support for any commercially available (i.e., FDA cleared or approved) devices (PAP and associated supplies). If a participant reports a device malfunction and/or device complaint to the sponsor support team (Verily User Success), the participant will be instructed to contact their DME provider.

The sponsor support team may contact study participants during study participation in order to troubleshoot issues with the VSA app, such as issues logging in or the app crashing.

10. Investigational Products

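### Section 5.6 does not separate low PAP use from protocol non-compliance as a ground for withdrawal, so the 90-day compliance rate can be biased upward if withdrawn participants leave the denominator

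*Combined protocol and SAP*

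**What the plan says.** Section 5.6 contains five statements that act together:

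- Ground for withdrawal: "The Investigator may withdraw the participant any time due to the non-compliance with respect to the provisions of the protocol". No threshold is given.
- Completion: "Participants will either satisfactorily complete all requirements set forth in the protocol or their participation in the clinical study will be prematurely terminated".
- Follow-up after withdrawal: "no new health information identifying him/her will be gathered after that date".
- Data already collected: "Information that has been gathered may still be used and given to others".
- Replacement, after any withdrawal or discontinuation before all activities are complete: "a new, qualified candidate may be enrolled in the study to compensate for the incomplete data set".

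The Protocol Summary, under Participant Duration, adds: "Active participation is defined as using the PAP device (PAP data collection) while completing the other study related activities".

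The secondary compliance endpoint in Section 5.1.2 is "Percent of participants who meet 90 day compliance success criteria, as defined by" at least 4 hours a night on 70% of nights in some run of 30 consecutive days within the first 90. Unlike the completion rates listed just above it, it names no denominator beyond participants. Time from therapy initiation to this threshold is a primary endpoint (Sections 5.1.2 and 12).

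The visible part of Section 12 plans averages, standard deviations and confidence intervals for the time endpoints across all participants. It gives a planned enrolment of about 50 to 200 and says the sample will probably be too small for hypothesis testing. The text after that is redacted.

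**The concern.** Low PAP use is the failure outcome of the compliance endpoint. If it can also count as protocol non-compliance, the investigator may end a participant's follow-up because of the outcome being measured. The study is open and single-group, and Table 1 schedules compliance monitoring and protocol deviation assessment in the same types of contact, so such decisions would be made with emerging compliance in view. No control arm exists in which a distortion would show up as a difference.

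Two results are exposed. The compliance rate rises if the people removed also leave the denominator. The time-to-threshold endpoint can lose its late achievers, because follow-up stops at withdrawal. The study's stated aim is a baseline understanding of how the program performs, so these descriptive estimates are its main product.

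**Working it through.** **No plan figure to reproduce.** The documents state no expected compliance rate, withdrawal rate or derived sample size. The inputs p, w, d and v below are assumptions.

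**1. Withdrawn participants leave the denominator.** Let p be the true compliance rate and w the share of non-compliers withdrawn. Per person started, p succeed and w(1 − p) are removed, so the expected rate is p / (1 − w(1 − p)).

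| w | p = 0.60 | Rate | Bias (points) |
|---|---|---|---|
| 0.10 | 0.60 / 0.96 | 0.625 | +2.5 |
| 0.30 | 0.60 / 0.88 | 0.682 | +8.2 |
| 0.50 | 0.60 / 0.80 | 0.750 | +15.0 |

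Over p = 0.50 to 0.75, the bias is +1.9 to +2.6 points at w = 0.10 and +10.7 to +16.7 points at w = 0.50.

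**2. Replacement is not the cause.** The formula is the same with or without replacement, provided replacements face the same withdrawal rule. If replacements are made only once, the inflation is slightly smaller. Take 100 starters with 60 achievers and 10 non-achievers withdrawn: dropping them gives 60/90 = 66.7%, and replacing them with people who also achieve 60% gives (60 + 6)/100 = 66%.

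**3. Everyone who started stays in.** With withdrawn non-compliers counted as failures, the rate is p = 0.600. A simulation of 4,000 runs at p = 0.60 and w = 0.30 gave 0.602 (N = 50) and 0.601 (N = 200) with everyone kept, and 0.682 at both sizes with withdrawn people dropped and replaced.

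**4. Some withdrawn people would have succeeded later.** Let d be the share of starters withdrawn and v the share of those who would have gone on to succeed. Counting them as failures gives p − dv. With d = 0.12 and v = 0.25 this is 0.60 − 0.03 = 0.570, a downward bias of 3 points. Dropping them gives 0.570/0.88 = 0.648, still 4.8 points too high. Dropping inflates the rate whenever v < p.

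**5. Size against precision.** The 95% half-width at p = 0.60 is 1.96 × √(0.24/N): 13.6 points at N = 50 and 6.8 points at N = 200. At w = 0.10 the bias (+2.5) is well inside both. At w = 0.30 (+8.2) it exceeds the half-width at N = 200. Filling 200 places at w = 0.30 takes 200/0.88 ≈ 227 starters, about 27 of them replaced; filling 50 takes about 57, with about 7 replaced.

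**6. Time to threshold.** Seventy percent of 30 nights is 21 nights. Someone with no use through night 69 who then uses PAP adequately on nights 70 to 90 (21 nights) still qualifies. Withdrawing low users before then removes the longest times, which would shorten the mean among achievers. No size is given because the documents offer no distribution of these times.

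**The case against.** **The denominator may already be settled.** Visible Section 12 covers only the primary time endpoints before the redaction starts, and a rule for the secondary endpoints may follow. Section 5.6 lets data already gathered be used, and enrolling a further candidate can mean adding people, not swapping them. This stands. A reader might infer that the rate *is* biased upward, but the documents support only that it *can be*.

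**PAP non-use as a ground for withdrawal is an inference.** The active-participation definition describes a study period. Section 7.3 treats PAP as clinical care. The responses to non-compliance actually described are outreach (Table 1) and supplemental visits (Section 6.2.5). This lowers the likelihood of such withdrawals, but the complete-or-terminate sentence in Section 5.6 pulls the other way, and nothing visible excludes them.

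**Other tempting extensions fail.** A reader might infer that the rate of using PAP at least once is inflated too. Its denominator is already everyone prescribed a device, so a withdrawn never-user stays in. A reader might also count Section 9 ("Alternatively, the sponsor may choose to exit the participant without providing a replacement device") as selection on the endpoint. That exit follows equipment failure and could remove compliers as readily as non-compliers.

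**Fixing the denominator would be enough.** It would be for the rate. It would not be for time to threshold, where a late achiever withdrawn early is lost however the rate is scored.

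**The stakes are modest.** The rate is secondary and descriptive, reasons for discontinuation are already documented on the case report form, and the larger biases need a large share of non-compliers to be withdrawn. This stands and limits the severity.

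**Conclusion.** The concern holds in conditional form. Section 5.6 visibly permits withdrawal and replacement without separating low PAP use from protocol non-compliance, and PAP use underlies one secondary and one primary endpoint. If withdrawn participants leave the compliance denominator, an assumed true rate of 60% would be reported as about 62.5% to 75.0% when 10% to 50% of non-compliers are removed. If all starters are kept and withdrawals count as failures, there is no upward bias and possibly a small downward one. Which case applies cannot be read from the visible text. Independently of the denominator, early withdrawal can remove late achievers from the time endpoint. This should be fixed, with moderate confidence.

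**What to change.** 1. In Section 5.6, state that low PAP or app use is a study outcome and is not by itself protocol non-compliance for the purpose of study withdrawal and replacement. Align the complete-or-terminate sentence with this. Leave withdrawal for medical interest and by participant choice unchanged.
2. In Sections 5.1.2 and 12, unless the redacted text already does so, define the compliance denominator as everyone prescribed PAP, or everyone who started it, with the choice fixed in advance. Include withdrawn and replaced participants, so that replacements add to the denominator and never substitute.
3. In the main analysis, count anyone withdrawn without a documented qualifying 30-day window as not meeting the criterion. Add a sensitivity analysis for exits unrelated to use, such as device failure, because this scoring can bias the rate slightly downward.
4. Report withdrawals and replacements by reason.

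The cost is protocol and SAP wording. The reported rate may be somewhat lower, and the denominator may exceed nominal enrolment where replacements are made. If the redacted text already contains items 2 and 3, the sponsor need only confirm it; item 1 is still needed.
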